### 10.5 Individuals reviewing the data

Research members will review data.

### 10.6 Frequency of review of cumulative data

Cumulative data will be reviewed once patient surveys are collected and patient information is de-identified.

### 10.7 Statistical tests

The proportion of positive cultures will be determined using Fisher’s exact test to compare the positive culture rates. Ordinal or interval Demographic data will be compared between the two groups using parametric vs nonparametric tests depending on their normality. Nominal data will be compared using Fisher’s exact test or contingency table.

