## 7.0 Study Design and Procedures

### 7.1 Study Design

[figure not shown]
Thirty patients will be identified in the clinic with indications for open or arthroscopic shoulder surgery. Patients will be informed about the current prospective study and written consent will be obtained. Both shoulders of each patient will be included for the study; the surgical side shoulder will serve as a “Treatment shoulder” while the normal non-operative contralateral shoulder will serve as a “Control shoulder”. All patients will receive a wireless, low-level microcurrent-generating antimicrobial dressing (JumpStart® Antimicrobial Wound Dressing, Arthrex, Inc., Naples, Florida, USA) (Figure 1) and hydrogel on the posterior aspect of their Treatment shoulder 2 days prior to their surgery. A small amount of hydrogel will be applied to the undersurface of JumpStart dressing. The adhesive dressing will make the JumpStart stick to the skin. The dressing will be kept on the shoulder until the time the patient is transferred to the operating room on the day of surgery. The dressing will be applied by a member of the research team at clinic. Upon transfer to the operating room on the day of surgery, the JumpStart dressing will be removed from the Treatment shoulder. All patients will receive routine preoperative IV antibiotics (either Cefazolin or Clindamycin) at least 5 minutes prior to skin incision and a routine operative skin preparation for both shoulders using standard, alcohol-based preparation (ChloraPrep, 2% chlorhexidine gluconate and 70% isopropyl alcohol; Enturia, El Paso, TX, USA) immediately before skin incision in the operating room.

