At the time of the surgery, 2 separate 3-mm punch biopsy specimens will be taken from the posterior shoulder skin of both shoulders using a disposable biopsy punch (Disposable Biopsy Punch; Robbins Instruments, Chatham, NJ, USA) (Figure 2) . The biopsy sites will be closed with an adhesive tape (Steri-Strip, 3M, Maplewood, MN, USA) and covered with a routine gauze dressing. Samples will be transferred directly into separate sterile specimen containers from the biopsy punches using clean, sterile forceps. Specimens will then be transferred directly to a single laboratory for culture. Anaerobic and aerobic culture substrates will be used and held for 14 days for *P. acnes* only, given literature that shows *P. acnes* can grow on either substrate. Anaerobic culture plates will be incubated for 4 days and broth cultures for 14 days before concluding that the final report is negative. To serve as a “negative control,” while wearing sterile gloves, in the first 20 patients, a sterile culture swab will be opened in the operating room, wiped through the air, and sealed in a specimen container. Chocolate plate will serve as a settle plate in the OR suite for 10 minutes and incubated for 4 days. Data will include demographic data of patients, positive culture rates, and the number of days before resulting in positive culture. All culture results will be reviewed and the patient will be marked positive if any of the cultures were positive. Patients will be scheduled for postoperative, routine follow-up visits. The rest of patient care will follow our current routine standard care without any modifications or interventions.

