**8.2 Sample size determination**

A priori sample size calculation was performed using some of the previously published data. Assumptions were made as follows: the primary outcome measure was the intraoperative culture results (e.g. positive, negative) for *P. acnes* by evaluating bacterial cultures from two skin biopsies obtained from the posterior aspect of the shoulder at the time of the surgery. Based on a previous study, the positive culture rate in untreated shoulders was set at 60%. We set the minimally clinically significant difference (MCID) of positive culture rate at 30% (a half of 60%) as a previous study described. Using a two-tailed McNemar test for two dependent groups with a power of 0.8 and an alpha of 0.05, the priori sample size calculation suggested a total of 30 patients for the study.

Probability		Treatment shoulder		
		Positive culture	Negative culture	
Control shoulder	Positive culture	0.25	0.35	0.6
	Negative culture	0.05	0.35	0.4
		0.3	0.7	1

Exact - Proportions: Inequality, two dependent groups (McNemar)

Options:  $\alpha$  balancing:  $\alpha/2$  on each side, approximation

Analysis: A priori: Compute required sample size

Input: Tail(s) = Two

Odds ratio = 7

$\alpha$  err prob = 0.05

Power (1- $\beta$  err prob) = 0.8

Prop discordant pairs = 0.4

Output: Lower critical N = 2.000000

Upper critical N = 10.000000

Total sample size	=	30
Actual power	=	0.8180007
Actual $\alpha$	=	0.0385742
Proportion p12	=	0.3500000
Proportion p21	=	0.0500000

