### 8.3 Statistical methods

If at least one of the two cultures from a shoulder turns positive, that shoulder will be counted as a “positive culture” shoulder. The results of the two cultures from each shoulder will be McNemar test will be used to compare the proportions of positive culture rates between paired shoulders. Ordinal or interval Demographic data will be compared between the two groups using parametric vs nonparametric tests depending on their normality. Nominal data will be compared using Fisher’s exact test or contingency table. The negative control data will be analyzed in comparison to the results of the treatment and normal control shoulders.

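### Section 10.7 assigns Fisher's exact test to the positive-culture comparison, contradicting the paired McNemar test on which sections 8.2 and 8.3 rest; under the plan's own table this costs 14.4 points of power

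*Combined protocol and SAP*

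**What the plan says.** Three current sections of the combined protocol and SAP name a test for the same outcome, culture positivity by shoulder.

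- Section 8.2 (sample size): "Using a two-tailed McNemar test for two dependent groups with a power of 0.8 and an alpha of 0.05". The software printout in the same section is labelled "Exact - Proportions: Inequality, two dependent groups (McNemar".
- Section 8.3 (statistical methods): "McNemar test will be used to compare the proportions of positive culture rates between paired shoulders". It does not say whether the exact, mid-p, continuity-corrected or uncorrected version is meant.
- Section 10.7 (statistical tests, within the data and safety monitoring plan): "The proportion of positive cultures will be determined using Fisher’s exact test to compare the positive culture rates".

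The design is paired by patient. Section 7.1 states: "Both shoulders of each patient will be included for the study"; the operated shoulder is treated and the other is the control.

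Two smaller wording points sit beside this. Section 7.1 defines positivity by patient ("All culture results will be reviewed and the patient will be marked positive if any of the cultures were positive"), whereas section 8.3 defines it by shoulder. Sections 8.3 and 10.7 also plan demographic comparisons between two groups without saying which groups these are.

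**The concern.** Fisher's exact test compares two independent samples. Here the 30 treated and 30 control shoulders come from the same 30 people, and the table in section 8.2 assumes that a patient's two shoulders tend to agree: it puts the probability that both are positive at 0.25, against 0.6 × 0.3 = 0.18 if they were independent. An unpaired test discards that information.

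An analyst who followed section 10.7 would be complying with the protocol while running a test for which the trial was not sized. With two named tests, and no version of McNemar's test named in 8.3, the choice of primary test could also remain open until the cultures have been read.

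The Fisher sentence cannot be read as covering demographics only. Section 10.7 gives culture rates a sentence of their own and then deals with demographic and nominal data separately.

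**Working it through.** **Inputs (section 8.2).** N = 30 pairs; two-sided alpha 0.05; positive rate 0.60 in control and 0.30 in treated shoulders. Cell probabilities are: both positive 0.25, control only 0.35, treatment only 0.05, neither 0.35. The discordant proportion is 0.35 + 0.05 = 0.40, and the probability that a discordant pair favours treatment is 0.35/0.40 = 0.875 (odds ratio 7).

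**Step 1: reproduce the plan's figure.** Fix the discordant pairs at 30 × 0.40 = 12 and reject if the count X favouring treatment is ≤ 2 or ≥ 10.

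- Alpha = 2 × P(X ≤ 2 | 12, 0.5) = 2 × (1 + 12 + 66)/4096 = 0.0386, as printed.
- Power = P(X ≥ 10 | 12, 0.875) + P(X ≤ 2 | 12, 0.875) = 0.2713 + 0.3453 + 0.2014 + a negligible term = 0.8180, as printed.

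**Step 2: compare the tests on the same basis.** In the trial the number of discordant pairs is random. Power is therefore the sum, over all tables (a, b, c, d) with a + b + c + d = 30, of the multinomial probability 30!/(a! b! c! d!) × 0.25^a × 0.35^b × 0.05^c × 0.35^d wherever the test gives p ≤ 0.05. Exact McNemar uses p = 2 × P(Bin(b + c, 0.5) ≤ min(b, c)), capped at 1. Fisher's test uses the marginal counts a + b and a + c, each out of 30.

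| Test | Power |
|---|---|
| Fisher's exact | 56.9% |
| McNemar, exact | 71.3% |
| McNemar, continuity-corrected | 71.0% |
| McNemar, mid-p | 79.4% |
| McNemar, uncorrected | 79.5% |

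The like-for-like loss is 71.3 − 56.9 = 14.4 points. Exact McNemar alone is significant with probability 0.1444, and Fisher alone with probability 0.0006.

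**Step 3: dependence on the correlation.** Keep the 60% v 30% margins and vary the probability that both shoulders are positive.

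| Both positive | Discordance | Fisher | Exact McNemar |
|---|---|---|---|
| 0.18 (independent) | 54% | 56.1% | 55.1% |
| 0.20 | 50% | 56.3% | 58.6% |
| 0.22 | 46% | 56.6% | 62.8% |
| 0.25 (plan) | 40% | 56.9% | 71.3% |
| 0.275 | 35% | 57.3% | 80.7% |

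**Step 4: type I error.** The plan gives no null table, so these are assumptions, each with 60% positive in both shoulders.

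| Discordance | Fisher | Exact McNemar |
|---|---|---|
| 20% | 0.1% | 1.3% |
| 40% | 1.5% | 2.4% |
| 48% (independent) | 2.6% | 2.7% |

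**Step 5: an example at the plan's critical split.** Take 8 patients positive in both shoulders, 10 in control only, 2 in treatment only and 10 in neither, so 18/30 v 10/30 positive. Exact McNemar gives p = 0.039 and Fisher p = 0.069, so in this example the conclusion turns on which section is followed.

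**The case against.** The strongest reply is that the intended test is clear. Section 8 is the statistical plan, its sizing and methods both name McNemar, and the design is paired. The Fisher sentence sits in the safety-monitoring section, close to a mention of patient surveys that the trial does not otherwise describe, so it may be leftover text. On that reading the 14.4-point loss arises only if someone follows 10.7 over section 8. This is a fair inference, but the document does not say so, and 10.7 is current text addressed to the culture rates.

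Second, the open choice of test does little harm to the type I error. Under the three nulls above, the chance that at least one of Fisher, exact, mid-p or uncorrected McNemar gives p ≤ 0.05 is 4.8%, 4.3% and 4.7% (in the order of the table). This stands for those scenarios: the case rests on lost power and an unsettled primary test, not on false positives.

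Third, the Step 5 example is not general. With a 10 v 2 split, Fisher is also significant when the number positive in both shoulders is 0–3 or 15–18; the tests disagree only for 4–14. That range includes the plan's expected count, 30 × 0.25 = 7.5.

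Fourth, section 8.2's printout already points to the exact version, so naming it in 8.3 is a clarification. The exact version also has less power than mid-p (71.3% v 79.4%), so adopting it is a choice the sponsor should make knowingly.

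Last, section 1.2 also mentions days to positive conversion within the primary outcome. Culture positivity is, however, the only outcome sized and the only one given a named between-shoulder test.

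**Conclusion.** The concern holds and must be fixed. Section 10.7 names an unpaired test for the primary paired comparison, against sections 8.2 and 8.3, and no text resolves the conflict. Following 10.7 would give 56.9% power where the exact McNemar test has 71.3%. These figures assume the plan's own table and 30 evaluable pairs. The loss grows with the correlation between a patient's shoulders: none if they are independent, about 2 points at 50% discordance, 14.4 at the plan's 40% and about 23 at 35%. The gap between 71.3% and the stated 81.8% comes from fixing the discordant pairs at 12 and is not part of this point.

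**What to change.** **Section 10.7:** replace the Fisher sentence with: *Positive culture rates will be compared between paired shoulders with the McNemar test as specified in section 8.3.*

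**Section 8.3:** name the version: *An exact two-sided McNemar test at alpha 0.05 will compare the proportion of culture-positive shoulders between the treatment and control shoulders of the same patients.* This matches the calculation in 8.2. If the sponsor prefers another version, it should be named before any cultures are read.

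**Minor clarifications:** in section 7.1, replace the patient-level rule with: *Each shoulder will be marked positive if either of its two biopsy cultures is positive.* In sections 8.3 and 10.7, state which two groups the demographic comparisons concern. If they are the two shoulders of the same patients, describe demographics once for the 30 patients and drop the tests.

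**Cost:** wording only. Patients, specimens and sample size are unchanged.

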### 10.8 Suspension of research

Research will be suspended if project is determined unsafe at any time for patients.

## 11.0 Risks

Loss of patient information during the project. Loss of confidentiality of paper and electronic data. Possible risks of skin biopsies include acute bleeding, localized pain, infection, scarring, and healing problems. Possible risks of dressing use include irritation, increased pain, temporary discoloration of the skin, and allergic reactions to silver or zinc.

## 12.0 Potential Benefits to Subjects and Others

### 12.1 Potential Benefits to Subjects

Microcurrent-generating antimicrobial device has been observed, in vitro, to exhibit bactericidal effect in the presence of antibiotic and multidrug resistant clinical wound isolates. Antimicrobial prophylaxis using this device can reduce length of hospital stay, compromised function, and financial burden while increasing quality of living.

### 12.2 Potential Benefits to Others

Preventing periprosthetic joint infection post-operation can reduce financial burden on the health care system and prevent unnecessary, prolonged use of antibiotics as antimicrobial prophylaxis.

## 13.0 Sharing Results with Subjects

The patients will be notified if infections are suspected and will be followed up with appropriate revision surgery or any required additional procedures for infections.

## 14.0 Subject Stipend (Compensation) and/or Travel Reimbursements

No compensation will be provided for this study.

## 15.0 Economic Burden to Subjects

### 15.1 Costs

No cost to the patients.

### 15.2 Compensation for research-related injury

It is the policy of the institution to provide neither financial compensation nor free medical treatment for research-related injury. In the event of injury resulting from this research, medical treatment is available but will be provided at the usual charge. Costs for the treatment of research-related injuries will be charged to subjects or their insurance carriers.

## 16.0 Resources Available

### 16.1 Facilities and locations

Recruitment will occur at Penn State Bone and Joint Institute or Penn State Camp Hill office. Eligible patients will be identified at clinic during their clinical encounter with [name]. All surgeries will be done at Hershey Medical Center and HOSC.

### 16.2 Feasibility of recruiting the required number of subjects

This project aims to recruit 30 patients for this study. Patients will be followed up by the Department of Orthopedics. Patients who decline participation in the study will be removed and a new patient will be recruited.

### 16.3 PI Time devoted to conducting the research

PI has dedicated research days to ensure time to complete project.

**16.4 Availability of medical or psychological resources**

Orthopedics clinic will schedule patients if they require an appointment during this study.

**16.5 Process for informing Study Team**

Team members have monthly meetings in person to review protocols.

## **17.0 Other Approvals**

**17.1 Other Approvals from External Entities**

No additional approvals required.

**17.2 Internal PSU Committee Approvals**

**Check all that apply:**

Anatomic Pathology – Hershey only – Research involves the collection of tissues or use of pathologic specimens. Upload a copy of HRP-902 - Human Tissue For Research Form on the “Supporting Documents” page in CATS IRB. This form is available in the CATS IRB Library.

Animal Care and Use – All campuses – Human research involves animals and humans or the use of human tissues in animals

Biosafety – All campuses – Research involves biohazardous materials (human biological specimens in a PSU research lab, biological toxins, carcinogens, infectious agents, recombinant viruses or DNA or gene therapy).

Clinical Laboratories – Hershey only – Collection, processing and/or storage of extra tubes of body fluid specimens for research purposes by the Clinical Laboratories; and/or use of body fluids that had been collected for clinical purposes, but are no longer needed for clinical use. Upload a copy of HRP-901 - Human Body Fluids for Research Form on the “Supporting Documents” page in CATS IRB. This form is available in the CATS IRB Library.

Clinical Research Center (CRC) Advisory Committee– All campuses – Research involves the use of CRC services in any way.

Conflict of Interest Review – All campuses – Research has one or more of study team members indicated as having a financial interest.

Radiation Safety – Hershey only – Research involves research-related radiation procedures. All research involving radiation procedures (standard of care and/or research-related) must upload a copy of HRP-903 - Radiation Review Form on the “Supporting Documents” page in CATS IRB. This form is available in the CATS IRB Library.

IND/IDE Audit – All campuses – Research in which the PSU researcher holds the IND or IDE or intends to hold the IND or IDE.

Scientific Review – Hershey only – All investigator-written research studies requiring review by the convened IRB must provide documentation of scientific review with the IRB submission. The scientific review requirement may be fulfilled by one of the following: (1) external peer-review process; (2) department/institute scientific review committee; or (3) scientific review by the Clinical Research Center Advisory committee. NOTE: Review by the Penn State Hershey Cancer Institute Scientific Review Committee is required if the study involves cancer prevention studies or cancer patients, records and/or

tissues. For more information about this requirement see the IRB website at:  
<http://www.pennstatehershey.org/web/irb/home/resources/investigator>

## 18.0 Multi-Site Research

### 18.1 Communication Plans

Not a multi-site research project.

### 18.2 Data Submission and Security Plan

Not a multi-site research project.

### 18.3 Subject Enrollment

Not a multi-site research project.

### 18.4 Reporting of Adverse Events and New Information

Not a multi-site research project.

### 18.5 Audit and Monitoring Plans

Not a multi-site research project.

## 19.0 Adverse Event Reporting

### 19.1 Adverse Event Definitions

For drug studies, incorporate the following definitions into the below responses, as written:	
Adverse event	Any untoward medical occurrence associated with the use of the drug in humans, whether or not considered drug related
Adverse reaction	Any adverse event caused by a drug
Suspected adverse reaction	Any adverse event for which there is a reasonable possibility that the drug caused the adverse event. Suspected adverse reaction implies a lesser degree of certainty about causality than "adverse reaction". 

Reasonable possibility. For the purpose of IND safety reporting, "reasonable possibility" means there is evidence to suggest a causal relationship between the drug and the adverse event.

Serious adverse event or Serious suspected adverse reaction	Serious adverse event or Serious suspected adverse reaction: An adverse event or suspected adverse reaction that in the view of either the investigator or sponsor, it results in any of the following outcomes: Death, a life-threatening adverse event, inpatient hospitalization or prolongation of existing hospitalization, a persistent or significant incapacity or substantial disruption of the ability to conduct normal life functions, or a congenital anomaly/birth defect. Important medical events that may not result in death, be life-threatening, or require hospitalization may be considered serious when, based upon appropriate medical judgment, they may jeopardize the patient or subject and may require medical or surgical intervention to prevent one of the outcomes listed in this definition.
Life-threatening adverse event or life-threatening suspected adverse reaction	An adverse event or suspected adverse reaction is considered "life-threatening" if, in the view of either the Investigator (i.e., the study site principal investigator) or Sponsor, its occurrence places the patient or research subject at immediate risk of death. It does not include an adverse event or suspected adverse reaction that had it occurred in a more severe form, might have caused death.
Unexpected adverse event or Unexpected	An adverse event or suspected adverse reaction is considered "unexpected" if it is not listed in the investigator brochure, general investigational plan, clinical protocol, or elsewhere in the current IND application; or is not listed at the

suspected adverse reaction.	specificity or severity that has been previously observed and/or specified.
------------------------------------	---

For device studies, incorporate the following definitions into the below responses, as written:	
Unanticipated adverse device effect	Any serious adverse effect on health or safety or any life-threatening problem or death caused by, or associated with, a device, if that effect, problem, or death was not previously identified in nature, severity, or degree of incidence in the investigational plan or IDE application (including a supplementary plan or application), or any other unanticipated serious problem associated with a device that relates to the rights, safety, or welfare of subjects.

#### **19.2 Recording of Adverse Events**

All adverse events (serious or non-serious) and abnormal test findings observed or reported to study team believed to be associated with the study drug(s) or device(s) will be followed until the event (or its sequelae) or the abnormal test finding resolves or stabilizes at a level acceptable to the investigator.

An abnormal test finding will be classified as an adverse event if one or more of the following criteria are met:

- The test finding is accompanied by clinical symptoms
- The test finding necessitates additional diagnostic evaluation(s) or medical/surgical intervention; including significant additional concomitant drug treatment or other therapy

**NOTE:** Simply repeating a test finding, in the absence of any of the other listed criteria, does not constitute an adverse event.

- The test finding leads to a change in study drug dosing or discontinuation of subject participation in the clinical research study

The test finding is considered an adverse event by the investigator.

